7.0 Dose Modifications

Induction: no dose reductions allowed.

Re-induction: Dose reductions may be allowed in the setting of hepatotoxicity as follows:

- For SGPT/SGOT 150-300 U/L **OR** bilirubin 1.5-3.0 mg/dL, reduce daunorubicin dose to 45 mg/m²/day.
- For SGPT/SGOT > 300 U/L **OR** bilirubin > 3.0-5.0 mg/dL, reduce daunorubicin dose to 30 mg/m²/day.

Consolidation: No dose reductions allowed for Cycle 1 except in the instance of renal dysfunction, as follows:

- For creatinine greater than 2 mg/dL or calculated creatinine clearance of < 50 mL/min, decrease cytarabine dose to 1,000 mg/m²/dose.
- For creatinine greater than 3 mg/dL or calculated creatinine clearance of < 30 mL/min, change cytarabine to 400 mg/m²/day IV infusion over 24 hours daily for 5 days.

For consolidation cycles beyond Cycle 1, doses of cytarabine may be reduced by 750 mg/m²/day for the following reasons:

- Grade 3-4 non-hematologic toxicity
- Severe life-threatening infection

If toxicity persists, cytarabine dose may be reduced by an additional 750 mg/m²/day.

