6.0 Treatment Plan

	Study entry ^a	INDUCTI ON: (up to 2 Cycles) *At each treatment [*]	INDUCTION CYCLE 1		INDUCTION CYCLE 2 (**if needed as indicated by bone marrow aspirate and biopsy)			CONSOLIDATION : (up to 4 Cycles for CBF AML) *At each treatment*	Post- treatment	Follow-up or relapse			
			*Additional Activities*		*Additional Activities*					*Additional Activities*			
			Day 4	Day 14 (+/- 2 days)	Prior	Day 3	Day 14 (+/- 2 days)						
Informed consent	X												
Demographics	X												
Medical history	X												
Concurrent meds	X												
Physical exam	X												
Vital signs	X	X							X				
Height, Weight, M ²	X												
Performance Status	X												
Bone marrow aspirate & biopsy ^b	X			X ^b			X ^b			X ^b			
CBC w/diff, platelets	X	X							X	X			
Serum chemistry ^c	X ^d	X							X				
Troponin I (Appendix E)	X ^d		X ^e			X ^e							
B-HCG ^f	X												
ECHO (Appendix E)	X ^h				X ^g					X ^g			
MRI without contrast (Appendix E)	X									X	X		
Adverse event evaluation	X	X	X	X	X	X	X	X	X	X	X		

^a Completed within 28 days prior to registration unless otherwise indicated.

^b On day 14 (+/- 2 days) of Induction Cycles 1 and 2, at recovery to confirm response, and at completion of all treatment, then as clinically indicated.

^c Total bilirubin, BUN, creatinine, SGOT[AST], SGPT[ALT]

^d Draw after consent signed and prior to day 1 treatment; results not required to start treatment.

^e On day 4 of treatment of Induction Cycle 1, and on day 3 of Induction Cycle 2 for those with persistent leukemia.

^f Serum pregnancy test (women of childbearing potential).

^g Limited ECHO with strain measures

^h Full 3D ECHO

CYTARABINE PLUS CONTINUOUS INFUSION DAUNORUBICIN, WITH CARDIAC MRI MONITORING, INDUCTION THERAPY FOR ADULTS WITH ACUTE MYELOID LEUKEMIA; A FEASIBILITY STUDY

Wake Forest Baptist Comprehensive Cancer Center (WFBCCC) CCCWFU 22616

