6.1 Treatment Administration

Treatment will be administered on an inpatient basis. Reported adverse events and potential risks are described in Section 9. No investigational or commercial agents or therapies other than those described below may be administered with the intent to treat the patient's malignancy.

Agent	Dose	Route	Schedule	Cycle Length
Induction				
Cytarabine	100 mg/m ² /day	IV infusion	Days 1-7	14 days
Daunorubicin	60 mg/m ² /day	IV infusion	Days 1-3	
Re-induction (if needed)				
Cytarabine	100 mg/m ² /day	IV infusion	Days 1-5	14 days
Daunorubicin	60 mg/m ² /day	IV infusion	Days 1-2	
Consolidation (up to 3 cycles, or up to 4 cycles for CBF AML)				
Cytarabine	<60 yrs: 3,000 mg/m ² /day ≥ 60 yrs: 1,500 mg/m ² /day	IV infusion over 3 hours, every 12 hours	Days 1,3,5	≥ 28 days

Induction: This study regimen will follow the standard 7+3 regimen of cytarabine and daunorubicin, with the modification of daunorubicin administered as continuous infusion rather than bolus. Baseline troponin I, full 3D ECHO, and MRI without contrast will be performed prior to treatment.

For troponin determination, the study will use either the TnI-Ultra™ assay, Siemens, Munich Germany or the Beckman Coulter Access 2 AccuTnI+3 assay for detection of troponin I. While the assays are comparable, every effort will be made to test all samples on the current Institutional standard troponin I testing platform (TnI-Ultra assay, Siemens). If the TnI-Ultra assay becomes unavailable either because of changing Institutional standards or product availability the Beckman Coulter Access 2 AccuTnI+3 assay will be utilized. The brand of assay and results will be recorded for each test on the Cardiac Function Worksheet.

Patients will have a bone marrow aspirate and biopsy on day 14 (± 2 days).

Re-induction: A second induction course may be given if the day 14 bone marrow aspirate and biopsy shows bone marrow cellularity as $\geq 10\%$ and $> 5\%$ leukemic blasts. Those requiring re-induction will undergo a limited ECHO with strain measures prior to treatment. This abbreviated cycle will consist of cytarabine on days 1-5 and daunorubicin on days 1 and 2, with a troponin I measure on day 3 and a bone marrow biopsy on day 14 (± 2 days). Patients not achieving a remission after 2 induction attempts will be removed from study.

CYTARABINE PLUS CONTINUOUS INFUSION DAUNORUBICIN, WITH CARDIAC
MRI MONITORING, INDUCTION THERAPY FOR ADULTS WITH ACUTE MYELOID

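### Section 7.0 states no re-induction daunorubicin rule for bilirubin above 5.0 mg/dL, so read literally the dose can return from 30 to 60 mg/m²/day

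*Combined protocol and SAP*

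**What the plan says.** The dose table in section 6.1 gives daunorubicin 60 mg/m²/day at induction (days 1-3) and at re-induction. For re-induction the text adds: "This abbreviated cycle will consist of cytarabine on days 1-5 and daunorubicin on days 1 and 2".

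Section 7.0 then sets different reduction rules by phase:

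- For the first course: "Induction: no dose reductions allowed".
- For the second course: "Re-induction: Dose reductions may be allowed in the setting of hepatotoxicity as follows".
- The milder re-induction tier applies at SGPT/SGOT 150-300 U/L or "bilirubin 1.5-3.0 mg/dL, reduce daunorubicin dose to 45 mg/m²/day".
- The more severe tier is: "For SGPT/SGOT > 300 U/L OR bilirubin > 3.0-5.0 mg/dL, reduce daunorubicin dose to 30 mg/m²/day".

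No further hepatic tier follows. Sections 3.1 and 3.2 contain no bilirubin or transaminase limit. The schedule in section 6.0 places serum chemistry, which includes bilirubin and both transaminases, at study entry and at each induction treatment. Only the study-entry draw carries footnote d: "Draw after consent signed and prior to day 1 treatment; results not required to start treatment".

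**The concern.** The bilirubin limb of the more severe tier is capped at 5.0 mg/dL and nothing takes over beyond the cap. The transaminase limb of the same tier is open-ended. So is the most severe renal tier for consolidation cytarabine in the same section (creatinine above 3 mg/dL or clearance below 30 mL/min). The cap therefore looks like a drafting gap, since no reason for it is given.

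The situation is foreseeable. Re-induction follows a full course of cytarabine, and section 9.2 lists abnormal hepatic function as very common (above 10%) with conventional-dose cytarabine. Chemistry is scheduled at the second induction cycle, so staff would have a bilirubin value with no rule to apply to it.

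Safety is one half of the primary objective in section 2.1.1, and section 1.1 describes daunorubicin cardiotoxicity as cumulative. A dosing rule that can be read in more than one way at its most severe end matters in such a trial.

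**Working it through.** The plan states no figure to reproduce here. The check is to apply section 7.0 literally and see which dose results.

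**Inputs**

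- Unreduced dose: 60 mg/m²/day (section 6.1 table).
- Daunorubicin days: 3 at induction, 2 at re-induction (section 6.1).
- Milder tier, 45 mg/m²/day: SGPT/SGOT 150-300 U/L or bilirubin 1.5-3.0 mg/dL (section 7.0).
- More severe tier, 30 mg/m²/day: SGPT/SGOT above 300 U/L or bilirubin above 3.0 and up to 5.0 mg/dL (section 7.0).

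**Assumptions**

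- A patient who matches no tier stays at the unreduced dose.
- Where both tiers match, the lower dose applies. Section 7.0 does not say so.
- Permitted reductions are taken.
- The laboratory values below are illustrative.

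**Re-induction dose, mg/m²/day**

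| SGPT/SGOT (U/L) | Bilirubin 1.0 | 2.0 | 4.0 | 5.0 | 5.1 | 8.0 |
|---|---|---|---|---|---|---|
| 100 | 60 | 45 | 30 | 30 | 60 | 60 |
| 200 | 45 | 45 | 30 | 30 | 45 | 45 |
| 400 | 30 | 30 | 30 | 30 | 30 | 30 |

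**Course dose just above against at 5.0 mg/dL** (daily dose × 2 days)

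- SGPT/SGOT 100: 2 × 60 = 120 against 2 × 30 = 60 mg/m²; ratio 120/60 = 2.0.
- SGPT/SGOT 200: 2 × 45 = 90 against 2 × 30 = 60 mg/m²; ratio 90/60 = 1.5. If the higher dose governed where both tiers match, this would be 90 against 90, ratio 1.0. So the figure lies between 1.0 and 1.5, depending on an unstated convention.
- SGPT/SGOT 400: 60 against 60 mg/m²; ratio 1.0. The open-ended transaminase limb holds the dose at 30 mg/m²/day.

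**Cumulative exposure.** Induction gives 3 × 60 = 180 mg/m². With SGPT/SGOT below 150 U/L, the two-course total is 180 + 60 = 240 mg/m² at bilirubin 5.0 mg/dL. It is 180 + 120 = 300 mg/m² just above, on the literal reading.

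**Induction.** The dose is 60 mg/m²/day at every bilirubin and transaminase value. There is no reversal within that course.

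**The case against.** The strongest reply is that the protocol is silent above 5.0 mg/dL and nowhere directs 60 mg/m²/day. Section 6.1 says a second course may be given, section 7.0 says reductions may be allowed, and section 6.5 ends treatment for unacceptable adverse events, intercurrent illness, or a condition the investigator judges unsuitable for more treatment. A clinician could well withhold the drug. This stands as far as it goes: the text permits the higher dose and does not mandate it. But neither section 6.5 nor the general exclusion for uncontrolled illness in section 3.2.8 names a hepatic threshold. Discretion to stop treatment does not supply a missing tier.

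A reader might also infer three stronger things that the documents do not support.

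- *That the bar on reductions at induction helps create the reversal.* It does not; everyone in that course has the same daily dose. Different rules for different courses are not in themselves a contradiction. Footnote d is consistent with the bar, because a result that cannot change the dose need not be awaited, and it covers only the study-entry draw.
- *That patients with the poorest liver function get the most drug.* This is false as a general statement. With bilirubin above 5.0 mg/dL and SGPT/SGOT above 300 U/L the stated dose is 30 mg/m²/day, the lowest in the section.
- *That the primary results are distorted.* Section 13.1 is a descriptive single-arm analysis with no comparison between dose levels, and the size of the affected subset is unknown. No effect on the results has been shown.

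**Conclusion.** The point holds as a gap in one line of section 7.0. At re-induction, bilirubin above 5.0 mg/dL falls under no stated rule. Read literally, the daily dose is then 60 mg/m² with SGPT/SGOT below 150 U/L, against 30 mg/m² at 5.0 mg/dL: a twofold difference, 120 against 60 mg/m² over the course. The difference is at most 1.5-fold at SGPT/SGOT 150-300 U/L and absent above 300 U/L.

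These sizes rest on the unreduced dose being the default when no tier matches, on permitted reductions being taken and, for the 1.5, on the lower dose governing where tiers overlap. How many of the planned 40 patients would be affected cannot be derived: the documents give neither a re-induction rate nor a bilirubin distribution.

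The gap should be closed before the rule is used, because it concerns patient safety and is cheap to correct. The phase-by-phase difference at induction is a separate matter of lower priority. It may be deliberate, but the protocol does not say so.

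**What to change.** The sponsor must reconcile section 7.0 with the section 6.1 dose table so that bilirubin above 5.0 mg/dL at re-induction falls under a stated rule. The choice of rule is clinical and belongs to the investigators; none is suggested here. The same edit could say which tier governs when a patient meets both.

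Separately, and with lower priority, the sponsor should confirm that three features are intended alongside the hepatic thresholds used at re-induction: the bar on reductions at induction, the absence of a hepatic eligibility criterion, and footnote d on the study-entry chemistry. One explanatory sentence would do if they are.

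The cost is a protocol amendment of a few lines. The sample size, visit schedule and analysis do not change.

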LEUKEMIA; A FEASIBILITY STUDY

Wake Forest Baptist Comprehensive Cancer Center (WFBCCC) CCCWFU 22616

Patients without bone marrow involvement at diagnosis will receive a second induction course if they have not cleared their soft tissue disease by day 14 (± 2 days).

If cellularity is $<10\%$ on day 14, a repeat bone marrow biopsy should be obtained as clinically indicated. Treatment response will be evaluated once ANC $>1,000 / \mu\text{L}$ and platelets $\geq 100,000 / \mu\text{L}$, but no later than day 42. If peripheral blood counts are inadequate (ANC $<1,000 / \mu\text{L}$, platelets $<100,000 / \mu\text{L}$) at the time of this bone marrow aspirate and biopsy, a repeat bone marrow aspirate and biopsy must be obtained to document complete remission at the time of peripheral blood count recovery (ANC $\geq 1,000 / \mu\text{L}$, platelets $\geq 100,000 / \mu\text{L}$) if > 1 week after "day 42" bone marrow study.

Physicians should consider earlier bone marrow exams in patients whose peripheral blood counts are not recovering or recovering sluggishly, as well as in patients whose day 14 bone marrow was suspicious for residual leukemia.

Consolidation: Patients in remission will receive high-dose cytarabine (days 1, 3, and 5) consolidation therapy for up to 3 cycles (except in the case of toxicity or receipt of stem cell transplant). Patients with core-binding factor (CBF) AML may receive 4 cycles of consolidation therapy. Therapy should be started as soon as possible (and within 14 days) after recovery from induction/re-induction therapy.

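### Consolidation cytarabine is given in inconsistent units in Sections 6.1 and 7.0, so under one of three readings the first renal reduction raises the dose at age 60 or over; the renal tiers are also written only for Cycle 1

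*Combined protocol and SAP*

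**What the plan says.** The treatment table in Section 6.1 gives consolidation cytarabine by age. Under 60 the entry is 3,000 mg/m²/day; for older patients it reads "≥ 60 yrs: 1,500 mg/m ² /day". The route is "IV infusion over 3 hours, every 12 hours", and the treatment days are 1, 3 and 5. The text of the same section adds: "Patients in remission will receive high-dose cytarabine (days 1, 3, and 5) consolidation therapy for up to 3 cycles". A fourth cycle is possible in core-binding factor AML.

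Section 7.0 then sets the reductions:

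- Cycle 1 is introduced by "Consolidation: No dose reductions allowed for Cycle 1 except in the instance of renal dysfunction, as follows". Two renal tiers follow.
- Tier 1: "For creatinine greater than 2 mg/dL or calculated creatinine clearance of < 50 mL/min, decrease cytarabine dose to 1,000 mg/m²/dose". It has no age split and does not change the 12-hourly schedule.
- Tier 2, for creatinine above 3 mg/dL or clearance below 30 mL/min: "change cytarabine to 400 mg/m²/day IV infusion over 24 hours daily for 5 days".
- Later cycles: "For consolidation cycles beyond Cycle 1, doses of cytarabine may be reduced by 750 mg/m²/day for the following reasons". The two listed reasons are grade 3-4 non-hematologic toxicity and severe life-threatening infection. A repeat is possible: "If toxicity persists, cytarabine dose may be reduced by an additional 750 mg/m²/day".

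The full dose and the toxicity step are therefore per day, and the first renal tier is per dose.

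**The concern.** Two infusions a day separate a per-day figure from a per-infusion figure by a factor of two. That is enough to turn a reduction into an increase in the older group, whose full dose is the lower one. The patient concerned has impaired renal function (creatinine above 2 mg/dL or clearance below 50 mL/min, but not yet in tier 2).

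Such a patient can be on the trial. Sections 3.1 and 3.2 set no creatinine or clearance limit and no upper age limit, and age 60 or over is a planned stratum in Sections 5.2.2 and 13.2. Section 9.2 warns of severe and sometimes fatal toxicity with high-dose cytarabine, so the dosing text should leave no room for guessing.

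The second issue is scope. Both renal tiers hang on the Cycle 1 sentence, while patients may receive three or four consolidation cycles. A patient whose clearance falls below 50 or 30 mL/min before a later cycle finds no renal threshold written for that cycle.

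**Working it through.** The protocol states no figure to reproduce here; the check is unit arithmetic.

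**Inputs.** From 6.1: 3,000 (under 60) and 1,500 (60 or over), printed as mg/m²/day; every 12 hours, so 2 infusions a day; 3 treatment days, so 2 × 3 = 6 infusions per cycle. From 7.0: tier 1 at 1,000 mg/m²/dose; tier 2 at 400 mg/m²/day for 5 days; toxicity step of 750 mg/m²/day, repeatable once.

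**Three readings of tier 1.**

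- A: 6.1 is a daily total as printed, and a dose in 7.0 is one infusion. Full dose per infusion = 6.1 figure / 2.
- B: 6.1 is meant per infusion, and a dose is one infusion. Full dose per infusion = 6.1 figure.
- C: 6.1 is a daily total, and /dose in 7.0 refers to that daily entry. Tier 1 per infusion = 1,000 / 2 = 500.

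Change = tier 1 / full dose − 1; cycle total = 6 × dose per infusion. All doses are in mg/m².

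| Reading | Age | Full dose per infusion | Tier 1 per infusion | Change | Cycle total |
|---|---|---|---|---|---|
| A | ≥60 | 750 | 1,000 | +33% | 4,500 to 6,000 |
| A | <60 | 1,500 | 1,000 | −33% | 9,000 to 6,000 |
| B | ≥60 | 1,500 | 1,000 | −33% | 9,000 to 6,000 |
| B | <60 | 3,000 | 1,000 | −67% | 18,000 to 6,000 |
| C | ≥60 | 750 | 500 | −33% | 4,500 to 3,000 |
| C | <60 | 1,500 | 500 | −67% | 9,000 to 3,000 |

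The rule goes the wrong way in one of six cells. Under B the direction is right, but the 6.1 table as printed gives half of what was meant: 9,000 instead of 18,000 mg/m² per cycle under 60, and 4,500 instead of 9,000 at 60 or over.

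**Tier 2.** 400 × 5 = 2,000 mg/m² per cycle. This is below every full-dose cycle total above (4,500, 9,000 or 18,000), so tier 2 is always a reduction.

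**Toxicity step at age 60 or over, applied twice.**

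- As printed, both per day: 1,500 to 750 to 0 mg/m²/day.
- 6.1 per infusion, step per day: 3,000 to 2,250 to 1,500 mg/m²/day.
- Both per infusion: 1,500 to 750 to 0 mg/m² per infusion.

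**Which unit was meant?** Section 6.1 calls the treatment high-dose. Section 9.2 describes high-dose schedules as 2.0 to 3.0 g/m² every 12 hours. Under B the under-60 dose is 3.0 g/m² per infusion, inside that range; as a daily total it is 1.5 g/m², below it. This points to B but does not settle it. Section 9.2 is general adverse-reaction text about a 12-dose schedule, and the older group's dose is below 2.0 g/m² under every reading (0.75 or 1.5 g/m²). Section 10.3 gives only a 24-hour infusion route for cytarabine and does not help.

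**The case against.** The strongest objection is that the 33% rise depends on reading A, which is probably not what was intended and which contradicts the rule's own verb. Nobody can raise a dose and also obey an instruction to decrease it. A pharmacist who met the conflict should raise a query. This stands. A reader might infer that staff who follow the protocol would escalate cytarabine in older patients with renal impairment. The documents do not support that: the text contradicts itself under reading A and is not a clear order to give more.

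Reading C is also open, since the 6.1 column headed Dose contains per-day entries. It is the less natural reading, because tier 2 in the very next line is written per day, but it cannot be excluded.

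On later cycles, a reader might infer that no renal provision exists after Cycle 1, or that full dose is required. Neither holds. Renal toxicity that reaches grade 3-4 falls under the listed non-hematologic reason. The tiers are not forbidden in later cycles. A cycle can also be delayed (cycle length is at least 28 days), withheld for toxicity (6.1) or ended (6.5). What remains is narrower: the creatinine and clearance thresholds do not carry over, and the step that is available is optional and different in size.

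Finally, consolidation cytarabine is not the modification under test. That is true, and it limits the point to safety and clarity.

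**Conclusion.** The point holds as an inconsistency of units with a possible safety consequence. The mismatch between 6.1 and 7.0 is certain, and no other section resolves it. The consequence depends on the reading. There is a 33% increase per infusion at age 60 or over if 6.1 holds daily totals and a dose is one infusion. There is a correct reduction, but a halved printed daily dose for every consolidation patient, if 6.1 is meant per infusion. There is a correct reduction if /dose refers to the daily entry. Some correction is therefore needed whichever unit was meant, and the documents do not confirm which it was.

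Separately, the renal thresholds are written for consolidation Cycle 1 only. That leaves an incomplete instruction for up to two later cycles, or three in core-binding factor AML.

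How many of the 40 patients would be affected cannot be estimated from the documents. No sample size, endpoint, feasibility measure or analysis depends on this.

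**What to change.** Amend Sections 6.1 and 7.0 as follows.

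1. State the 6.1 consolidation doses and every cytarabine dose and step in 7.0 in one explicit unit, with tier 2 kept as the 24-hour infusion it already describes. If per infusion is intended, write 3,000 and 1,500 mg/m² per infusion every 12 hours; tier 1 at 1,000 mg/m² per infusion is then below full dose in both age groups. If daily totals are intended, tier 1 must be under 750 mg/m² per infusion at age 60 or over.
2. State the unit of the 750 step and check that two steps do not reach zero at age 60 or over. With 6.1 per infusion and the step kept per day, two steps leave 1,500 mg/m²/day. If the dose and the step share a unit, whether per day or per infusion, the older group needs a smaller step or a single step.
3. Add one sentence that both renal tiers apply to every consolidation cycle.

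The cost is a short amendment, after the investigator confirms the intended unit. Sample size, endpoints and analysis do not change.

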8.0 Measurement of Effect

8.1 Antitumor Effect

Response and progression will be evaluated in this study criteria defined by Cheson et al.¹⁴ (see Appendix D).

8.2 Definitions

- Study Regime: Completion of the critical study regime tasks will be tracked by research staff and recorded as “Yes” or “No” in Appendix E, The Cardiac Function form. The tasks that should be recorded in this manner are the following:
 - The daunorubicin infusion (Induction):
 - if this is not completed in 72 hours +/- 1, record as “No”,
 - If the infusion is completed within these parameters record “yes”.
 - If “No”, record the total infusion amount and time taken to administer.

**CYTARABINE PLUS CONTINUOUS INFUSION DAUNORUBICIN, WITH CARDIAC
MRI MONITORING, INDUCTION THERAPY FOR ADULTS WITH ACUTE MYELOID
LEUKEMIA; A FEASIBILITY STUDY**

Wake Forest Baptist Comprehensive Cancer Center (WFBCCC) CCCWFU 22616

- ECHO (at pre-induction visit, *post-treatment (pre-discharge), 3 month follow-up or relapse):
 - Record “Yes” or “No” if the patient completes or does not complete the ECHO at each visit.
 - *indicates an additional assessment for those individuals requiring a second cycle of Induction therapy
- MRI (at pre-induction visit, 3 month follow-up or relapse, at 6 month follow-up or relapse):
 - Record “Yes” or “No” if the patient completes or does not complete the MRI at each visit.
- Evaluable for toxicity: All patients will be evaluable for toxicity from the time of their first treatment with daunorubicin.
- Persistent leukemia: Patients not achieving a remission after 2 induction attempts; these patients will be removed from the study.
- Disease-free survival: calculated for patients who achieve CR and measured from the date of CR until relapse from CR or death. Observation is censored at the date of last follow-up for patients last known to be alive without report of relapse.
- Time to death: calculated from date of study registration to date of death due to any cause. Patients last known to be alive are censored at date of last contact.

